## **Statistical Analysis Plan**

Data analysis: Aim 1. We will estimate the (1) differences in the effects of first-stage interventions (NS vs brochure), (2) differences in the effects of second-stage interventions (BC vs NS among those who complete testing and referral vs CD among testing decliners), and (3) differences in the effects of selected adaptive interventions on acceptance of testing and adherence to NJ recommendations. For the differences between NS and brochure, cross-tabulations of the interventions with each outcome will be generated, and crude odds ratios comparing the two will be calculated. For the effects of second-stage and third-stage interventions, we will perform a similar analysis as that for the first-stage interventions but on corresponding subsets as indicated in the specific comparison groups. The estimation of effects of embedded adaptive interventions will use weighted and replicated estimation techniques. Under these procedures, the data set will be restructured wherein an individual's outcome will be replicated in the data set depending on the number of adaptive interventions consistent with this outcome. Since randomization at both stages is based on equal probabilities, weighting is not necessary. The restructuring of the data set as described allows the utilization of standard statistical software for parameter estimation and hypothesis testing. A generalized linear model using logistic regression will be performed where estimation of model parameters will be done using generalized estimating equations due to the presence of replicated subjects. We will then use tests of contrasts to compare selected adaptive interventions. The analysis of the adaptive interventions will be done using PROC GENMOD in SAS. To adjust for baseline characteristics and test for their moderating effects, we will incorporate these terms and their interactions with first-stage, second-stage, and adaptive interventions in their respective models. Only the baseline characteristics will be used for adjustment, as outcomes of the first-stage intervention are biased if incorporated into this model. Odds ratios, 95% CI, and Wald's test for the effect of interventions and covariates will be obtained from these results. Sex/gender and race/ ethnicity will be among these covariates that we will consider for adjustment and moderation analysis.

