## **Methods for additional analyses (e.g., subgroup analyses)**

Aim 2: To identify other predictors of these outcomes, we will include these variables as covariates using logistic regression analysis. We will model probabilities of testing behavior (completed vs testing decliners) and adherence to NJ recommendations as functions of the first-stage intervention and other covariates in the logistic regression analysis.

**Qualitative component analysis:** Critical dialog sessions and in-depth interviews will be digitally audio-recorded and transcribed. Data will be entered into Atlas.ti, a qualitative data processing program. Analysis rooted in phenomenology and grounded theory will include continuous coding, comparison, and recoding to yield categories and connect experiences and themes. The analysis will focus on participant reports about their experiences with the intervention, barriers to testing and adherence to NJ recommendations, and suggestions on how to address these barriers.

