**Methods in analysis to handle protocol non-adherence and any statistical methods to handle missing data**

We will perform an intent-to-treat analysis of the data. Subjects will be grouped according to how they are randomized. The multiple imputation strategy described will be adapted [43]. This uses a time-ordered nested conditional imputation strategy with multiple imputation of missing values. In this approach, the fully conditional specification (FCS) imputation framework wherein a separate model for each variable is fitted will be applied. We will consider the time ordering of the data. For example, observed baseline variables will be used to impute for missing data from the first-stage results. Then, the imputed and observed values of the first-stage results will be used in conjunction with baseline variables to impute missing values for the second-stage results. We will examine the distribution of missing data according to intervention groups, covariates (e.g., demographic characteristics, adherence, reason for discontinuation), outcome variables, and time. We will determine whether the missing data pattern is not inconsistent with the missing-at-random (MAR) mechanism. We will also check whether the amount of missingness is monotonic over time. The R software packages mice and pan will be used for imputation.

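### Does the single mention of third-stage interventions undermine the SAP's decision not to weight the adaptive-intervention analysis?

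*SAP*

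**What the plan says.** The Aim 1 paragraph of the SAP (section Statistical Analysis Plan) lists three targets: first-stage effects (NS vs brochure), second-stage effects ("BC vs NS among those who complete testing and referral vs CD among testing decliners"), and contrasts of selected adaptive interventions.

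The first two are handled by cross-tabulations and crude odds ratios. The sentence extending that method to later stages opens "For the effects of second-stage and third-stage interventions" and says the work is done as for the first stage, "but on corresponding subsets as indicated in the specific comparison groups".

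The third target has its own method. Estimation "will use weighted and replicated estimation techniques": each outcome is replicated once for every adaptive intervention it is consistent with, and a logistic model is fitted by GEE. The weights are then set aside: "Since randomization at both stages is based on equal probabilities, weighting is not necessary".

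Elsewhere the SAP has two stages only. Baseline characteristics enter with "their interactions with first-stage, second-stage, and adaptive interventions". In the missing-data section, first-stage results and baseline variables are used "to impute missing values for the second-stage results", and the sequence ends there.

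**The concern.** The reason given for omitting weights covers two stages, yet the paragraph that gives it also speaks of a third. The text does not say who would enter a third stage, whether it would be randomized, or with what probabilities.

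This could matter because unweighted replication is valid only if every path through the design has the same product of randomization probabilities. If a subset were randomized once more, its members would be consistent with fewer adaptive interventions and would be under-represented in each. The regime rates, and the contrasts between regimes that are the third target of Aim 1, could then be biased in a direction that depends on who was re-randomized. Weights known by design would prevent this, and they cost one variable in the planned GENMOD step.

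A smaller point sits beside it. Aim 2 models "testing behavior (completed vs testing decliners" as a binary outcome. With that coding, acceptance of testing cannot vary in the BC vs NS comparison, which is made among people who have all completed testing.

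**Working it through.** **1. The plan's own statement, two stages.** Inputs from the SAP's Aim 1 paragraph: two first-stage options, two second-stage options for testers, two for decliners, equal probabilities. The path weight is 1 / (product of randomization probabilities):

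- Tester: 1 / (1/2 × 1/2) = 4
- Decliner: 1 / (1/2 × 1/2) = 4

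The weight is constant, so the no-weighting statement is reproduced. In a simulated two-stage data set of 670 participants (logistic GEE, independence working correlation, robust variance), coefficients were 0.095829, 0.542168 and 0.545852, and robust standard errors 0.126095, 0.164435 and 0.142266. Both sets were identical with and without weights. Only model-based standard errors would respond to a constant weight.

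**2. Other readings with no effect.** If everyone were randomized 1:1 a third time, the weight would be 8 for all. If a third stage were not randomized, it would stay at 4.

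**3. The reading that would matter.** Suppose only late testers are randomized again, 1:1, and the compared regimes distinguish the options. Let p be first-stage testing, q later uptake among decliners, and x = (1 − p)q. The true regime rate is T = p + x. Unweighted replication gives (p + x/2) / (1 − x/2). All rates below are assumptions; none is in the documents.

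| p | q | T | Unweighted | Difference (points) | Simulated 95% CI coverage, unweighted |
|---|---|---|---|---|---|
| 0.3 | 0.4 | 0.58 | 0.44/0.86 = 0.512 | −6.8 | about 62% |
| 0.5 | 0.3 | 0.65 | 0.575/0.925 = 0.622 | −2.8 | about 88% |
| 0.7 | 0.2 | 0.76 | 0.73/0.97 = 0.753 | −0.7 | about 94% |

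Coverage is from 20,000 runs with 670/2 = 335 participants in the first-stage arm and sandwich variance on the logit scale. Weighted coverage was about 95% in all three rows.

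If the remaining decliners were re-randomized instead (T = 0.58 before the third stage, assumed third-stage uptake 0.10), the sign reverses. The true rate is 0.58 + 0.42 × 0.10 = 0.622, and the unweighted rate is (0.58 + 0.021) / (0.58 + 0.21) = 0.761.

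**4. What step 3 needs.** Four things must hold together: a third stage exists, it is randomized, only a subset enters it, and the compared adaptive interventions distinguish its options. The documents state none of them. The last is doubtful in the table's example, because a late tester has already tested and a later option cannot change that. If testing regimes are not split by the third option, every path has probability 1/4 again and the unweighted rate is 0.30 + 0.28 = 0.58, the true value.

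**5. Where the term sits.** The third-stage sentence governs crude odds ratios within subsets, which need no path weights. The no-weighting sentence governs the replicated GEE. The two follow-up interviews (Protocol, section 8) also fit two stages.

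**The case for a change.** The strongest case for acting is that the wording conflict is real, the documents alone cannot settle it, and inverse-probability weights are harmless under two equal stages. The weighted analysis would cost nothing if the term is a slip and would protect the contrasts if it is not. In one assumed scenario with late testers re-randomized, two regimes with the same true rate of 58% are declared different in 14.4% of simulated trials unweighted, against 5.1% weighted.

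The second-stage phrase can also be parsed so that decliners receive CD only. Path probabilities would then be 1/4 for testers and 1/2 for decliners, and weights would matter even with two stages. With p = 0.3 and q = 0.4 the unweighted rate would be (0.15 + 0.28) / (0.15 + 0.70) = 0.43/0.85 = 50.6% instead of 58.0%.

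The arithmetic stands, and so does the inconsistency in wording. The inference to a change does not. Weights cannot be calculated until it is known who is randomized, when and with what probability. Once that is known, the choice between weighting and not weighting is automatic. The CD-only parse strains the sentence, which reads naturally as two parallel pairs, one for testers and one for decliners. The absence of a fuller design description is weak evidence too: Protocol section 10 says the consent document carries the study description, and consent pages were removed before review.

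The point about testers also stands, but it corrects itself. A cross-tabulation of BC vs NS against completed testing has an empty column, which leaves adherence as the informative outcome. Protocol section 8 speaks of at least one COVID test per participant, so a later test is a possible outcome as well.

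**Conclusion.** The concern does not call for a change. For the design the documents describe, with two equal randomizations and testers and decliners both re-randomized, the no-weighting rule is correct and the effect of adding weights on estimates and robust standard errors is exactly zero. Naming the weighted-and-replicated method and then noting that its weights are constant is not a contradiction.

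The third-stage wording appears once, against two-stage language in the aims, the weighting sentence, the moderation models and the imputation sequence, and is best taken as a clerical slip. The unnamed working correlation and variance estimator are details that analysts fill sensibly: the SAP chooses GEE because subjects are replicated, which points to robust variance.

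This conclusion rests on there being no third randomization confined to a subset, and on decliners being randomized between referral and CD. If either failed, the bias could be several points and of either sign, but that would be a different design from the one documented.

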This study is funded by the National Institutes of Health (NIH) as a supplement to our parent study optimizing *Community Wise*, an intervention to reduce substance use among formerly incarcerated men (R01 MD010629-01). The *Community Wise* optimization study is being conducted as community based participatory research (CBPR) with the Newark Community Collaborative Board (NCCB), a group of 20 community members, service providers, and researchers. NJCRI and the NCCB are the study's community partners, connected through the Principal Investigators. [name] is founder and chair of the NCCB; [name] is employed by NJCRI and is an original NCCB member. For this study, the NCCB will continue to use CBPR to optimize an adaptive intervention that will take people through the COVID-19 continuum of prevention, care and treatment, starting with outreach, followed by testing, prevention intervention for those testing negative, and recommendation to quarantine, treatment, and/or referral to community based services and/or contact tracing for those testing positive.

We will recruit an intent-to-treat sample of 670 adults and estimate 15% attrition for a final sample of 582. Participants in this clinical trial will be recruited through a combination of strategies. Fliers will be posted throughout Essex County in public spaces, restaurants, and health care clinics, and community based organizations. People who call the study will be encouraged to disseminate the study to their friends and family. The NCCB will reach out to their contacts and networks.

5. **PARTICIPANTS** (approximate number and all applicable categories):
Number of participants proposed: 670

 Female	 Inmates or prisoners
 Male	 Cognitive impaired persons
 Children (17 or younger)	 Non-English speaking persons
 Prisoners	
 Pregnant women	

6. **COST AND PAYMENTS: (Will there be incentives for this project?)**

Participants will receive \$30 for completing the baseline interview and \$40 for completing each of two follow-up interviews. A randomly selected sample of 35 participants who do not complete testing will receive \$50 for completing an in-depth, qualitative interview. Thus, an eligible participant could receive up to \$160 for completing all data collection activities.

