7. **ATTACHMENTS:** All relevant project materials and documents, including

- Surveys, questionnaires, interview instruments
- Informed Consent and Assent (if applicable) forms
- Letters of approval on letterhead from cooperating agencies, schools, boards of education, etc.
- Debriefing statement or explanation sheet if applicable
- Participant recruitment materials (e.g., fliers, advertisements)
- Other:

8. **CONFIDENTIALITY OF DATA:** how data will be stored and collected

Data will be generated and collected through interpersonal computer assisted interviews, computer assisted self-interviews, group session audio recordings, in-depth qualitative interviews and SARS antigen tests for COVID-19. Each participant will complete an initial telephone screening, a computer-assisted baseline and two follow-up interviews (2 weeks and 5 weeks post

baseline) and at least one COVID test. The electronic files generated through data collection and the test results will be identified by code numbers only and kept in password-protected and HIPAA-compliant devices and cloud storage, separate from identifying information and available only to project staff. This helps to ensure that no identifying information will be disclosed in the unlikely event that computerized data are stolen or otherwise seen by unauthorized persons. All identifying electronic data will be destroyed immediately after data collection is completed. Signed consent forms and audio recordings will be kept for 3 years after study completion. De-identified electronic data will be kept indefinitely. Study participants may ask at any time to have recordings of their interview destroyed by calling/e-mailing one of the Principal Investigators at the numbers provided in the informed consent forms.

9. RISKS AND BENEFITS: Describe Risks and Benefits

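### The SAP's bar on adjusting for first-stage outcomes can be read to cover the second-stage comparisons, where its reason fails for any variable fixed before second-stage assignment

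*SAP*

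**What the plan says.** The SAP's Aim 1 analysis has three targets: the first-stage contrast (NS vs brochure), the second-stage contrasts ("BC vs NS among those who complete testing and referral vs CD among testing decliners"), and the embedded adaptive interventions. The outcomes are acceptance of testing and adherence to the NJ recommendations. The second-stage contrasts are first analysed crudely: "we will perform a similar analysis as that for the first-stage interventions but on corresponding subsets as indicated in the specific comparison groups", which means cross-tabulations and crude odds ratios.

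Adjusted and moderation models come on top of that. On baseline characteristics the SAP says "we will incorporate these terms and their interactions with first-stage, second-stage, and adaptive interventions in their respective models", and then restricts what may enter: "Only the baseline characteristics will be used for adjustment, as outcomes of the first-stage intervention are biased if incorporated into this model".

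Two facts about timing matter. Assignment is random at each stage ("Since randomization at both stages is based on equal probabilities, weighting is not necessary"), but neither document says when the second randomisation takes place. Protocol section 8 times the interviews from enrolment only: "a computer-assisted baseline and two follow-up interviews (2 weeks and 5 weeks post" baseline. Protocol section 4 describes different pathways after testing: "prevention intervention for those testing negative, and recommendation to quarantine, treatment, and/or referral to community based services and/or contact tracing for those testing positive".

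**The concern.** The SAP's warning is correct where the contrast starts at the first randomisation. Testing uptake and anything measured after it may be affected by NS or brochure, so conditioning on them distorts the first-stage effect. It also distorts comparisons of whole adaptive interventions.

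The second-stage contrasts start at the second randomisation, within a subset already defined by a first-stage outcome. Relative to that randomisation, anything already observed is a baseline variable. Applied there, the rule excludes legitimate covariates for a reason that does not apply.

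Three things are at stake. These comparisons run on subsets and so have fewer participants than the first-stage comparison. The excluded variables may predict adherence. And because moderator terms are confined to baseline characteristics, no model spelled out in the plan asks whether BC vs NS differs between people who tested positive and negative, although Protocol section 4 sends the two groups down different pathways.

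**Working it through.** **1. Which models the rule covers.** The restriction refers to a single model. The sentence before it lists three kinds ("incorporate these terms and their interactions with first-stage, second-stage, and adaptive interventions in their respective models"), and nothing exempts the second-stage ones. The broad reading is the more natural; the narrow one is possible.

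**2. Figures in the documents.** Protocol section 4 gives 670 enrolled, 15% attrition and 582 final. The enrolment figure reproduces as 582 × 1.15 = 669.3, rounded up to 670 (670 × 0.85 would be 569.5). The point does not depend on this. No second-stage sample size, adherence rate, effect size or power is stated, so every input in step 3 is an assumption apart from 582 as the base for subset size and two-sided alpha 0.05, which the 95% CI implies.

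**3. Gain if the covariate precedes assignment.** Assumed: 30%, 50% or 70% of 582 in the subset (175, 291, 407); 1:1 allocation; outcome 50% vs 65%; one binary covariate with 50% prevalence; Wald test.

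Crude, n = 291 (145.5 per arm):
- log OR = logit(0.65) − logit(0.50) = 0.619 (OR 1.86)
- SE = √[1/(145.5 × 0.25) + 1/(145.5 × 0.2275)] = 0.240
- power = Φ(0.619/0.240 − 1.96) = 73.1%

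Adjusted, covariate OR 4. The cell rates that keep 50% vs 65% overall are 33.3% and 66.7% (control) and 50% and 80% (active):
- conditional OR = 2.00, log OR 0.693
- information = Σ w₀w₁/(w₀ + w₁) over covariate levels, where w = 72.75 × p(1 − p): 16.17 × 18.19/34.35 + 16.17 × 11.64/27.81 = 15.33
- SE = 1/√15.33 = 0.255
- power = Φ(0.693/0.255 − 1.96), or 77.4% before rounding

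The same calculation over the range gives:

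| Covariate OR | Power, n = 175 | n = 291 | n = 407 | SE of log OR, n = 291 | Fall in variance of standardised risk difference |
|---|---|---|---|---|---|
| 1 (same as crude) | 51.5% | 73.1% | 86.2% | 0.240 | 0% |
| 2 | 52.6% | 74.3% | 87.0% | 0.244 | 2.8% |
| 4 | 55.7% | 77.4% | 89.4% | 0.255 | 10.5% |
| 10 | 62.6% | 83.7% | 93.5% | 0.283 | 25.0% |

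The SE of the log odds ratio rises with adjustment. Power improves because the conditional odds ratio moves further from 1 (1.86 to 1.89, 2.00 and 2.30).

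**4. Validity.** In 1,500 simulated null trials at n = 291, with a covariate (OR 4) measured before assignment, type I error was 4.7% crude and 4.3% adjusted (Monte Carlo standard error √(0.05 × 0.95/1500) = 0.6 points). The mean log OR was 0.010 in both.

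**5. The opposite timing.** With the covariate measured after assignment and carrying the whole effect, the mean log OR went from 0.19 crude to −0.01 adjusted. Adjustment removed the effect.

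**6. Test result alone.** Assume 10% positive, a 30-point difference in adherence and 67% adherent overall. The share of variance explained is 0.1 × 0.9 × 0.3² / (0.67 × 0.33) = 3.7%.

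**The case against.** Several objections stand and limit the point.

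- **Timing of the 2-week interview.** A reader might infer that 2-week adherence precedes second-stage assignment and is therefore a valid covariate. The documents do not say so. Second-stage options depend on completing or declining testing, which could happen well before week 2, and the SAP also mentions third-stage interventions, so week 2 may fall after second-stage treatment has begun. Excluding it would then be right. Nor does either document say that the 2-week interview records adherence.
- **Test result.** It exists only for completers, so it can serve BC vs NS but not referral vs CD. That it is known before assignment is plausible from the pathway but not stated. Its contribution to precision is small.
- **The plan is not invalid.** The crude odds ratios on the subsets are supported by randomisation. Adding prognostic covariates is an efficiency choice, and the SAP does give a reason for its rule, sound for two of the three kinds of model.
- **Precision.** It is tempting to say that the second-stage odds ratios lose precision. On the log-odds scale they do not (step 3).
- **Size.** A reader might infer a gain worth about one third more participants. That needs a 25% fall in variance (1/0.75 = 1.33), hence a covariate odds ratio near 10, which nothing in the documents supports.
- **Moderation.** The rule's wording concerns adjustment, the comparison subsets are not fully defined, and the Aim 2 covariates are not listed. So one cannot say that the plan prevents an analysis by test result, only that it does not specify one.

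What survives is that the rule as worded reaches models where its reason fails. The SAP's missing-data section already uses first-stage results to impute second-stage ones, so the plan itself treats them as informative.

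**Conclusion.** The point holds as a worthwhile, low-cost improvement, not as an error that invalidates a planned comparison. On its most natural reading the SAP excludes all first-stage outcomes from the adjusted second-stage models, for a reason that does not apply to variables observed before second-stage assignment.

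The size of the loss cannot be derived from the documents. With 291 in the subset and 50% vs 65%, it is 1.2 power points at a covariate odds ratio of 2, 4.3 at 4 and 10.6 at 10; it is nil if the covariate does not predict the outcome. Test result alone would cut variance by about 4%, so its main use is moderation. The conclusion depends on timing: for a value measured after assignment, the SAP's exclusion is correct.

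**What to change.** Revise the Aim 1 adjustment text as follows.

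1. Limit the exclusion of first-stage outcomes to the first-stage and adaptive-intervention models.
2. State when second-stage assignment occurs relative to the test result and the 2-week interview, and whether that interview records adherence.
3. Add wording such as: *In the adjusted second-stage models, variables observed before second-stage assignment are treated as baseline. Both comparisons will be adjusted for first-stage arm. BC vs NS will also be adjusted for antigen test result, if known before assignment. 2-week adherence will be included only if it is collected and measured before second-stage assignment.*
4. Report a standardised risk difference beside the conditional odds ratio, since adjustment changes what the odds ratio estimates.
5. Report BC vs NS adherence by test result as a moderation analysis.
6. Keep the crude second-stage odds ratios as planned.

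The cost is one SAP paragraph and two or three terms in models already planned. First-stage arm and test result need no new data; 2-week adherence needs none if the interview already records it.
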